3.6.6 Active Treatment-Blind Set

The Active Treatment-Blind Set (ATS) consists of all subjects who received at least 1 dose of active treatment (BKZ or ADA) during the ATP (Week 16 and after).

Disposition, demographics, and Baseline characteristics will be reported on the ATS. The ATS will also be used to report data from the ATP such as study treatment compliance and exposure, adverse events, treatment-emergent markedly abnormal (TEMA) data for vital signs and laboratory data and selected efficacy analyses.

In this analysis set, the order of treatment groups presented in tables from left to right will be:

- Placebo / BKZ 160mg Q4W
- BKZ 160mg Q4W

- ADA 40mg Q2W.

For safety data, the first 2 groups will also be summarized as “BKZ 160mg Q4W Total”.

3.6.7 Per Protocol Set

The Per-Protocol Set (PPS) will consist of all subjects in the RS who had no IPD or non-PD related to prohibited medications affecting the primary efficacy variable (only IPD/non-PD related to prohibited medications observed prior to Week 16 are considered for exclusion from the PPS). The deviations will be predefined and subjects with deviations will be evaluated during ongoing data cleaning and data evaluation meetings prior to unblinding of the data ([Section 3.5](#)). Exclusion from the FAS will be considered as an IPD that also results in exclusion from the PPS.

Supportive analysis of the primary efficacy variable will be performed on the PPS.

3.6.8 Pharmacokinetic Per-Protocol Set

The Pharmacokinetic Per-Protocol Set (PK-PPS) consists of all randomized subjects who received at least one dose of the BKZ and provided at least one quantifiable plasma concentration post-dose (ie: after first BKZ dose) without IPD that would affect the concentration.

PK variables will be analyzed for all subjects in the PK-PPS.

3.6.9 Radiographic Set

The Radiographic Set (RAS) will consist of all subjects in the RS who received at least 1 dose of IMP and have a valid radiographic image of the hands and feet (with an assessment performed by at least the 2 reviewers) at Screening.

The analysis of vdHmTSS will be performed on the RAS.

3.6.10 COVID-19-free Set

The COVID-19-free Set will consist of all subjects in the RS who had no COVID-19 impact up to the primary efficacy endpoint. This will be defined as subjects (up to Week 16):

- not having a COVID-19 related IPD
- not having an impact based on the COVID-19 eCRF
- not having an AE related to COVID-19 ([Section 10.2.6](#))
- not discontinuing due to COVID-19.

The disposition data, the primary efficacy endpoint and the secondary efficacy endpoints included in the testing hierarchy will be analyzed on the COVID-19-free Set.

3.7 Treatment assignment and treatment groups

It is expected that subjects receive treatment as randomized and hence safety analyses will be based on the SS, as randomized. However, after unblinding, study treatment received might be in some cases different from the randomized treatment. If subjects randomized to placebo received BKZ at any time during the DBP, then for safety analyses these subjects will be reallocated to the BKZ treatment group. If subjects randomized to placebo received ADA at any time during the DBP (but no BKZ), then for safety analyses these subjects will be reallocated to the ADA

treatment group. Subjects randomized to BKZ will only be reallocated to the placebo treatment group if they never received BKZ. Subjects randomized to ADA will only be reallocated to the placebo treatment group if they never received ADA.

Efficacy analyses will be performed according to randomization and not actual treatment received. Data collected after study treatment discontinuation will be listed only and not reported in table except in the context of the treatment policy analysis performed on the primary efficacy endpoint ([Section 8.1.4.5](#)).

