2.3.2.2 Double-Blind Treatment Period

After the Screening Period, subjects will attend a Baseline visit (Visit 2, Day 1).

At the end of the Baseline visit, subjects will be randomized according to a 3:2:1 ratio (stratified by region and bone erosion [0, \geq 1] at Screening) to receive 1 of the 3 following blinded treatments during the 16 weeks of the DBP:

- Bimekizumab 160mg sc Q4W
- Placebo
- Adalimumab 40mg sc Q2W.

The first administration of IMP will be delivered at the Baseline visit (Visit 2, Day 1).

During the 16 weeks of the DBP, IMP administration will be performed by unblinded study personnel every 2 weeks (allowed visit window between 12 to 16 days) from Day 1 through Week 16 (Visits 2 to 10).

For the BKZ group, active treatment will be administered every 4 weeks and placebo in between, to maintain the blind and still have an injection every 2 weeks.

Visit 10 (Week 16) ends the DBP, and the last assessments for that period are collected during that visit.

This period starts on the day of first dose administration of study drug (Visit 2) and ends at Week 16 (Visit 10) or at the Early Termination visit (ET Visit) for subjects withdrawn from the study before Week 16. This period should last 16 weeks maximum.

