7 MEASUREMENTS OF TREATMENT COMPLIANCE

Treatment compliance summaries will be provided:

- On the SS for the DBP, by randomized treatment and for all subjects.
- On the ATS for the ATP, by randomized treatment, for all BKZ treated subjects and for all subjects
- On the AMS for the AMP, by randomized treatment, for all BKZ treated subjects and for all subjects.

Due to the method of IMP administration, compliance will be examined in terms of completed injections. Treatment compliance will be calculated as:

$$\frac{\text{Total number of actual (completed) injections}}{\text{Total number of expected injections}} \times 100 \%$$

The total number of expected injections is derived relative to when the subject finishes treatment:

- If a subject completes the DBP, 8 injections are expected (every 2 weeks from Baseline to Week 16)
- If a subject completes treatment over the entire study, 26 injections are expected (every 2 weeks from Baseline to Week 50)
- If a subject discontinues early, then the number of expected injections is based on the time of early discontinuation relative to the dosing visits. This number will be calculated by determining the number of expected dosing visits prior to the date of early discontinuation. If the early discontinuation coincides with an expected dosing visit, this visit will be used to determine the number of expected injections.

A summary of percent treatment compliance categorized as <75% and $\geq 75\%$ will be provided by treatment group, as well as a by-subject listing of treatment compliance.

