AE summaries by PT will be ordered in terms of decreasing frequency for PT within the BKZ treatment group, and in the event of ties, PT will be sorted alphabetically.

TEAEs will be classified by period (DBP, ATP or AMP) according to their date of emergence.

Summary tables of TEAEs will be provided on:

- The DBP by treatment on the SS,
- The ATP by treatment and for all BKZ-treated subjects in the ATS,
- The AMP for all BKZ-treated subjects and the ADA group in the AMS.

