10.2.4.9 Summary table and figure

The incidence of the below safety topics of interest occurring during the Double-Blind Treatment Period will be reported in one summary table and displayed graphically.

- Serious infection (Terms included in SOC “Infections and Infestations”)
- Fungal infection
- Opportunistic infection
- Malignancy (Terms included in the SMQ “Malignant tumours (SMQ)”)
- Adjudicated major adverse cardiac events (MACE)
- Neutropenia
- Adjudicated suicidal ideation and behavior (SIB)
- Definite adjudicated IBD
- Definite or probable adjudicated IBD
- Anaphylactic reaction
- Hypersensitivity reaction
- Hepatic events and drug-induced liver injury

For each of the above categories, the summary table and the graph will include the incidence, the EAIR by treatment group and the risk difference (BKZ minus placebo) with its 95% CI.

The risk difference (RD) will be derived as follows:

$$RD = \frac{Ab}{Nb} - \frac{Ap}{Np}$$

The lower and upper CI bounds for RD will be calculated as follows:

$$RD - Z_{\alpha/2} * SE (RD), RD + Z_{\alpha/2} * SE (RD)$$

Where:

Ab / Ap = Number of subjects in the BKZ / Placebo group (Safety Set) affected by the event

Nb / Np = Number of subjects in the BKZ / Placebo group (Safety Set)

$Z_{\alpha/2}$ = Critical value from the standard normal distribution (1.96 for a 95% CI).

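### SAP 3.7 has no safety re-allocation between the two active arms, so a subject who received only the other active drug is counted under placebo or the randomised arm in the by-arm DBP tables

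*SAP*

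**What the plan says.** Section 3.7 starts from an as-randomised default: "It is expected that subjects receive treatment as randomized and hence safety analyses will be based on the SS, as randomized". It then recognises that treatment received may turn out to differ once the study is unblinded, and gives four exceptions for safety:

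- Placebo subjects who received BKZ at any time in the DBP move to BKZ.
- Placebo subjects who received ADA but no BKZ move to ADA. The condition reads "If subjects randomized to placebo received ADA at any time during the DBP (but no BKZ), then for safety analyses", followed by the move to the ADA group.
- The BKZ arm has a single rule: "Subjects randomized to BKZ will only be reallocated to the placebo treatment group if they never received BKZ".
- The ADA arm has the same rule with the drug name exchanged: "Subjects randomized to ADA will only be reallocated to the placebo treatment group if they never received ADA".

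The Safety Set (Section 3.6.3) requires one dose of any IMP, so a subject dosed with the wrong active drug is in it. Section 10.2 tabulates treatment-emergent events for "The DBP by treatment on the SS". Section 10.2.4.9 forms a DBP risk difference, BKZ minus placebo, whose numerators are defined as "Number of subjects in the BKZ / Placebo group (Safety Set) affected by the event".

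**The concern.** The two placebo rules follow the active drug received, and even rank the two active drugs when both were given. The two active-arm rules do not. They ask only whether the randomised drug was never received, and they name only placebo as a destination. They do not ask whether the other active drug was given instead.

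This leaves two situations without a correct outcome: randomised to ADA with only BKZ received, and randomised to BKZ with only ADA received. If such a subject has an adverse event, the by-arm DBP tables report it under placebo or under the wrong active drug. Placement in placebo is the worse outcome, because an event on an active drug then raises the comparator rate. The wording also lets two programmers place the same subject differently. Because Section 3.7 expects mismatches to surface after unblinding, the choice would be made with treatment codes known.

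**Working it through.** **Enumeration of Section 3.7.** Each randomised arm is crossed with the drug received.

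| Randomised | Active drug received | Safety group under 3.7 |
|---|---|---|
| Placebo | BKZ, with or without ADA (DBP) | BKZ |
| Placebo | ADA only (DBP) | ADA |
| BKZ | BKZ, with or without ADA | BKZ |
| BKZ | none | placebo |
| BKZ | ADA only | placebo (literal) or BKZ (necessary condition only) |
| ADA | ADA, with or without BKZ | ADA |
| ADA | none | placebo |
| ADA | BKZ only | placebo (literal) or ADA (necessary condition only) |

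In the fifth and eighth rows the drug received is not a possible outcome. No other section of the SAP gives an active-to-active rule.

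**Effect of one affected subject with one event on the DBP risk difference.** The plan gives no figure to reproduce. The inputs are the planned sizes in Section 2.3.1: BKZ 420, placebo 280, ADA 140. The shift is the risk difference as placed minus the risk difference with the subject under the drug received, in percentage points.

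With no other events:

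- ADA-randomised, BKZ only, placed in placebo: −(1/421 + 1/281) = −(0.24 + 0.36) = −0.59 after rounding the sum.
- ADA-randomised, BKZ only, left in ADA: −1/421 = −0.24.
- BKZ-randomised, ADA only, placed in placebo: −1/281 = −0.36.
- BKZ-randomised, ADA only, left in BKZ: +1/420 = +0.24.

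With an assumed 5% background (21 BKZ events and 14 placebo events):

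- ADA-randomised, BKZ only. Correct value: 22/421 − 14/280 = 0.23. In placebo: 21/420 − 15/281 = −0.34, a shift of −0.56. Left in ADA: 21/420 − 14/280 = 0, a shift of −0.23.
- BKZ-randomised, ADA only. Correct value: 21/419 − 14/280 = 0.01. In placebo: 21/419 − 15/281 = −0.33, a shift of −0.34. Left in BKZ: 22/420 − 14/280 = 0.24, a shift of +0.23.

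**Scale.** The 95% CI half-width is 1.96·√[r(1 − r)(1/420 + 1/280)], assuming the usual unpooled standard error and an equal rate r in both arms.

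| Assumed r | Half-width (points) | Shift if left in randomised arm | Largest shift if placed in placebo |
|---|---|---|---|
| 1% | 1.50 | 0.24, or 16% of it | 0.59, or 39% of it |
| 2% | 2.12 | 0.24, or 11% of it | 0.59, or 28% of it |
| 5% | 3.30 | 0.23, or 7% of it | 0.56, or 17% of it |

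The 1% and 2% rows use the shifts without background events; the 5% row uses those with the 5% background.

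**How the case could arise.** In the DBP "IMP administration will be performed by unblinded study personnel every 2 weeks", and Section 7 expects 8 injections over a completed DBP. Over the whole study, "If a subject completes treatment over the entire study, 26 injections are expected". One wrong injection among otherwise correct ones is mixed exposure and leaves the subject in the randomised arm. The case needs sustained mis-assignment or a very early stop. The SAP gives no dispensing-error rate.

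**The case against.** The strongest objection is that the case may be empty. It needs a subject with no dose of the randomised active drug and at least one dose of the other, in a trial where unblinded staff give the injections. Section 3.7 itself expects treatment as randomised. The sizes above apply per affected subject who also has the event in question. The risk difference is descriptive, no safety hypothesis is in the testing hierarchy, and efficacy follows randomisation. The subject would also be traceable: Section 5.3 summarises incorrect treatment or dose as a type of important protocol deviation with a by-subject listing, and Sections 10.1 and 10.2.1 list dosing dates and adverse events by subject. All of this stands and limits the severity. It does not make the rule right, because a listing does not correct the count in the table.

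A reader might infer two stronger points that the text does not support.

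- One is that the subject definitely stays in the randomised arm by default. Section 3.7 does not settle this. The subject meets the stated condition of never having received the randomised drug, so placebo is the more natural literal outcome.
- The other is that the subject is nowhere analysed under the drug received. Section 3.6.5 defines the BKZ total column as all BKZ-treated subjects, and Section 10.2 uses similar wording for the tables covering the active-treatment and active-medication periods. These set no allocation rule for the by-arm tables, but they are worded by treatment received, so the point cannot be extended to them.

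**Conclusion.** Wrong as written, minor. Followed as it stands, Section 3.7 misattributes a subject who received only the other active drug. On either reading, that subject is not counted under the drug received in the by-arm DBP safety tables or the BKZ-minus-placebo risk difference.

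The effect on that difference is 0.36 or 0.59 points per affected subject with an event if the subject goes to placebo, and 0.24 points if the subject stays in the randomised arm. These figures assume planned arm sizes and no other events; at a 5% background they are 0.34, 0.56 and 0.23. The number of affected subjects is unknown and probably zero or very small. No hypothesis test or efficacy result depends on it. Leaving mixed-exposure subjects in their randomised active arm is defensible and is not criticised here.

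**What to change.** Replace the two active-arm sentences in Section 3.7 with a rule for DBP safety analyses:

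- A subject randomised to BKZ or ADA moves to placebo if, and only if, neither BKZ nor ADA was received during the DBP.
- A subject who did not receive the randomised active drug during the DBP but did receive the other one is analysed under the active drug received.
- A subject who received both stays in the randomised active arm, as now.

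The limit to the DBP matters. The current active-arm sentences carry no time limit, whereas the placebo rules do. Without it, a subject given the wrong active drug throughout the DBP and the right one from Week 16 would count as having received the randomised drug, and would still be misplaced in the DBP tables. Writing the first condition as both necessary and sufficient removes the present ambiguity.

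The cost is one or two SAP sentences and the matching programming rule. No new data, tables or listings are needed.

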3.8 Center pooling strategy

The 4 geographic regions considered for the study are the ones used for randomization stratification:

- North America (Canada, USA)
- Western Europe (Belgium, France, Germany, Italy, Spain, United Kingdom)
- Eastern Europe (Czech Republic, Hungary, Poland, Russia)
- Asia (Australia, Japan) identified as “Asia” in all analyses.

The above regions will be the ones used when considering the region as factor in the efficacy analyses.

3.9 Coding dictionaries

Medical history and AEs will be coded using the Medical Dictionary for Regulatory Activities (MedDRA®) version 19.0. Medications will be coded using the World Health Organization Drug Dictionary (WHO-DD) version March-2021. Medical procedures will not be coded.

To maintain consistency across studies in the BKZ development program, the dictionary versions will be held constant to support consistency of coding in the regulatory submissions.

3.10 Changes to protocol-defined analyses

The following changes from the protocol will be considered:

- An additional supportive analysis for primary endpoint based on the analysis of the individual components of ACR will be performed using the Reference-Based imputation method.
- The main analyses of the secondary continuous variables included in the testing hierarchy will be performed using the Reference-Based imputation method.
- Proportion of subjects with a decrease of HAQ-DI from Baseline of at least 0.35 (HAQ-DI responders) in those subjects with HAQ-DI ≥ 0.35 instead of >0.35 .
- An additional subgroup based on the combination of concomitant methotrexate (MTX) and Baseline conventional disease modifying antirheumatic drug (cDMARD).
- Additional subgroup analyses will be performed on HAQ-DI responders at Week 16.
- Proportion of PsAID-12 responders (decrease from Baseline in PsAID-12 total score ≥ 3) in subjects with PsAID-12 total score ≥ 3 at Baseline instead of >3 at Baseline

- The subgroup analysis on BASDAI will be performed on the categories: <4 vs. ≥ 4 rather than ≤ 4 vs. >4 .
- The analysis of the proportion of responding subjects at Week 52 among those who responded at Week 16 will be extended to all post Week 16 visits (and not only at Week 52).
- The analysis of the proportion of FACIT-Fatigue subscale responders (subjects with a minimum clinically important difference for FACIT-Fatigue subscale score defined as an increase of ≥ 4) will be performed in subjects with FACIT-Fatigue subscale score ≤ 48 at Baseline.
- The time to ACR20/50/70 will be exclusively analyzed using observed cases data.
- The AMS is an analysis set that has been added for the analysis of safety variables.
- The ATS is an analysis set that has been added for the analysis of data collected during the ATP.

3.11 Changes related to COVID-19

The impact of the COVID-19 pandemic on study procedures/conduct as well as the efficacy and safety endpoints will be investigated, and additional analysis outputs will be provided as appropriate. These additional analyses were not planned as part of the original protocol as the pandemic was not ongoing at the time of protocol finalization. These additional analyses will include analyses by period of the COVID-19 pandemic (pre/during/post) as defined below:

- Pre-COVID-19 pandemic period: period prior to COVID-19 pandemic start date defined as 11-Mar-2020
- COVID-19 pandemic period: period from 11-Mar-2020 though the COVID-19 pandemic end date which is currently not defined at the time of approval of the SAP
- Post-COVID-19 pandemic period: period after the declaration of the end of the pandemic.

The additional analyses are described in the following sections:

- Subject disposition ([Section 5.1](#))
- Demographics and other baseline characteristics ([Section 6](#))
- Details of impacted visits and effects on collection and reporting of efficacy data ([Section 5.2](#))
- Protocol deviations ([Section 5.3](#))
- Efficacy analyses related to the hierarchy endpoints ([Section 8.1.4.8](#) and [8.2.3](#))
- Adverse events ([Section 10.2.6](#)).

4 STATISTICAL/ANALYTICAL ISSUES

4.1 Adjustments for covariates

The primary efficacy analysis will investigate the treatment effect, adjusting on the 2 randomization stratification variables:

- Region:
 - North America, Western Europe, Eastern Europe, Asia
 - or
 - North America, Eastern Europe, Western Europe + Asia if the percentage of randomized subjects is < 10% in either of the Asia or Western Europe regions
- Bone erosion (0, ≥ 1) at Baseline.

When adjusting on these 2 variables, a statistical model might not converge (ie: the likelihood maximization algorithm fails to converge). In that case, the statistical model will be run after dropping successively region and bone erosion at Baseline.

If a subject is stratified in the incorrect stratum (ie: the stratum recorded in the Interactive voice or web Response System differs from the actual stratum the subject belongs to), the actual stratum will be used for the analysis.

The secondary analyses will be adjusted on the same categorical factors as retained for the primary analysis. For continuous variables, Baseline value (of the variable of interest) will be also included as covariate where appropriate.

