8.1.2 Primary analysis of the primary efficacy variable

The primary efficacy variable will be analyzed for all subjects in the RS.

The primary endpoint is the ACR50 response at Week 16. The primary efficacy analysis will evaluate the composite estimand in the RS. The composite estimand combines the clinically meaningful improvement from Baseline in ACR50 response and not discontinuing study treatment early.

The following 4 attributes describe the estimand that will be used to define the treatment effect of interest for the primary efficacy analysis:

- Population = Subjects enrolled according to the protocol-specified inclusion/exclusion criteria and randomized to IMP.
- Subject-level outcome = ACR50 at Week 16.
- IE handling = An IE is defined as discontinuation of study treatment prior to Week 16. A composite strategy will be implemented in which a positive clinical outcome is defined as achieving ACR50 at Week 16 and not discontinuing study treatment through Week 16.
- Population-level summary measure = Conditional OR comparing BKZ to placebo.

Missing data at Week 16 that are not preceded by an IE, and any data after an IE will be imputed as non-responders. This results in a more traditional NRI approach and will be labeled as such throughout the SAP.

The statistical hypothesis for the ACR50 response at Week 16 is that the conditional OR for ACR50 response in the BKZ treatment compared to placebo treatment is equal to 1.

A logistic regression model will be used to assess the treatment effect on ACR50 response at Week 16. The model will include a fixed effect for treatment. The suitability of including randomization stratification variables (bone erosion at Baseline and region) will be assessed using Pearson and Deviance and The Hosmer-Lemeshow Goodness-of-Fit Tests (Hosmer and Lemeshow, 2000).

In the context of the Week 24 analysis, actual bone erosion at Baseline as a covariate will be based on data from the first set of reads. For Week 52 analysis, data from the second set of reads will be used.

P-values below 0.05 would lead to a reconsideration of the model to be used and if the logistic regression model is unable to converge the stratification variables will be dropped ([Section 4.1](#)). In that case, all supportive analyses as well as imputation models conducted for the primary endpoint will disregard these factors from their models.

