The country-specific analyses performed on subjects randomized in Japan will not consider the region factor as a covariate for the modelling.

Considering that the number of subjects randomized in Japan is low (less than 10% of the Randomized Set), statistical models might not converge. If a model (Logistic Model or Mixed model) is not converging, all related adjusted statistics and p-value will not be presented : “NE” for “Not Evaluable” will be displayed instead.

The SAS® PROC LOGISTIC will be used to run the logistic regression.

The summary table results will present the adjusted responder rates and the associated 95% CIs for the 3 treatment groups, the adjusted OR and the corresponding 95% CI for the comparison of BKZ versus placebo, the p-value that the OR=1 and the difference of response rate between BKZ and placebo and associated 95% CI. Comparisons of BKZ vs. placebo will be made using the 2-sided Wald test at a significance level of $\alpha=0.05$ (ie, H_1 in [Table 4-5](#)).

Any use of prohibited or rescue medications through Week 16 would constitute an important protocol deviation which would be accounted for when the sensitivity analysis based on the PPS is performed ([Section 8.1.4.1](#)).

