8.2.2 Primary analysis of secondary efficacy variables

The secondary efficacy variables will be analyzed for all subjects in the RS by treatment group (except for vdHmTSS for which the analysis will be performed on the RAS).

As indicated in [Table 4–5](#), there are 8 secondary endpoints included in the testing hierarchy that will be tested in a chronological order until one is failed to be statistically significant.

For the other secondary endpoints (secondary endpoints which are not part of the testing hierarchy), the p-values produced by the statistical models will be considered nominal since these endpoints are not controlled for multiplicity.

For the secondary composite and non-composite binary endpoints, the same estimand structure (composite estimand) as the one defined for the primary efficacy analysis of the primary efficacy endpoint ([Section 8.1.2](#)) will be used. The NRI approach for handling missing data and the same analysis model will be considered, and the analysis results will be presented similarly, with the exceptions that the analyses performed on pooled data from PA0010 and PA0011 subjects will consider the region and the study-id factor as possible covariates for the modelling.

The statistical hypothesis for the binary variables at Week 16 is that the conditional odds ratio in the BKZ group compared with placebo treatment group is equal to 1.

For the secondary continuous endpoints, the analysis will evaluate the hypothetical estimand as defined below:

- Population = Subjects enrolled according to the protocol-specified inclusion/exclusion criteria and randomized to IMP.
- Subject level outcome = variable as stated in [Section 2.2.1.2](#)
- IE handling = An IE is defined as discontinuation of study treatment prior to Week 16. A hypothetical strategy for addressing IE will be implemented. This estimand targets the treatment difference in a scenario where withdrawal from study treatment does not occur, such that outcomes for subjects without an IE are as observed, and outcomes for subjects with an IE are treated as though they had completed treatment through Week 16 but on Placebo. A MI strategy will be used to impute any missing data and observed data after IE which will be set to missing prior to running MI. Such data will be imputed using reference-based MI, in which the MI model is based on data from the Placebo group.

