8.3.2.3 Additional statistical analysis for other efficacy endpoints

Although statistical testing is not planned for other efficacy variables as per protocol, for selected other efficacy variables, it is of interest to perform statistical testing and calculate inferential statistics. The associated p-values will be considered nominal and not controlled for multiplicity.

For continuous variables, the MI-MCMC/monotone regression approach will be applied for the imputation model on the change from Baseline (hypothetical estimand). The analysis model will be based on ANCOVA with fixed effect of treatment, region, bone erosion at Baseline and Baseline value as covariates.

For responder variables, the analysis will follow the NRI approach (composite estimand). The analysis model will be based on a logistic model with fixed effect for treatment and bone erosion at Baseline and region as stratification variables.

Below is a list of other secondary efficacy variables for which these nominal p-values (with the timepoints in parentheses) will be calculated.

The results of these inferential tests (LSM differences for continuous variables, OR for binary variables, 95% CI and p-value) will be presented in a single table:

For the following endpoints, the p-value provided (based on the change from Baseline for continuous variables) will be based on the comparison of BKZ 160mg Q4W and placebo groups using the same statistical methods for binary variables as used for the primary analysis of ACR50 (Section 8.1.2) and for the continuous variables as used for the analysis of the ACR components (Section 8.1.4.4):

- ACR20/50/70 (Week 2, 4, 8, 12, 16)
- PASI75/90/100 (Week 2, 4, 8, 12, 16)
- ACR50/PASI90 composite (Week 2, 4, 8, 12, 16)
- ACR50/PASI100 composite (Week 2, 4, 8, 12, 16)
- TJC (Week 2, 4, 8, 12, 16)
- SJC (Week 2, 4, 8, 12, 16)
- MDA (Week 4, 8, 12, 16)
- PtAAP (Week 2, 4, 8, 12, 16)
- PsAQoL (Week 4, 16)
- PsAID-12 (Week 4, 16)
- FACIT-Fatigue subscale (Week 4, 16)
- WPAI-SHP (Week 16) (on observed data)
- VdHmTSS (Week 16)
- DAPSA (Low disease activity or better) “response” (Week 2, 4, 8, 12, 16)
- PsARC (Week 2, 4, 8, 12, 16).

For the following endpoints, 2 p-values will be provided one for the comparison of BKZ 160mg Q4W and Placebo / BKZ 160mg Q4W groups and one for the comparison of BKZ 160mg Q4W and ADA 40mg Q2W groups:

- ACR20/50/70 (Week 16, 24, 52)
- PASI75/90/100 (Week 16, 24, 52)
- ACR50/PASI90 composite (Week 16, 24, 52)

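### When an arm has no responders, dropping region and bone erosion cannot repair the logistic/Wald analysis; nominal early-visit p-values and odds ratios are exposed

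*SAP*

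**What the plan says.** Section 4.1 defines non-convergence as the case where "the likelihood maximization algorithm fails to converge", and the response is to remove covariates: "In that case, the statistical model will be run after dropping successively region and bone erosion at Baseline". Section 8.1.2 repeats this for the primary model: "if the logistic regression model is unable to converge the stratification variables will be dropped". The same section fixes the test: "Comparisons of BKZ vs. placebo will be made using the 2-sided Wald test at a significance level of" 0.05.

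This method is carried to other endpoints. For the secondary binary endpoints, which include PASI90 and IGA response at Week 4, Section 8.2.2 states: "The NRI approach for handling missing data and the same analysis model will be considered". Section 8.3.2.3 applies the primary method to early and high-threshold endpoints, for example "PASI75/90/100 (Week 2, 4, 8, 12, 16", and likewise to ACR70 and the ACR50/PASI90 and ACR50/PASI100 composites from Week 2. Sections 8.2.2 and 8.3.2.3 call these p-values nominal.

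The one other rule on non-convergence is for the Japan-specific tables: "If a model (Logistic Model or Mixed model) is not converging, all related adjusted statistics and p-value will not be presented", with NE shown instead. That governs display and is not an alternative test.

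**The concern.** Dropping covariates helps when a region or erosion category is too thin to estimate. It does not help when the empty cell belongs to the treatment comparison. With no responders in one arm, the likelihood keeps rising as the treatment log odds ratio goes to infinity, and the standard error grows faster than the estimate. The Wald statistic therefore shrinks toward zero as iteration proceeds, so the printed p reflects the stopping rule and not the data.

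At stake is the reporting of early skin and high-threshold responses, including two listed secondary variables (PASI90 and IGA at Week 4). Following the plan literally could put a p near 1 beside a clear difference. The alternative would be to choose another test after the data have been seen.

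**Working it through.** **The plan's own figure.** ACR50, 43.8% versus 16%, with 420 and 280 subjects (Section 2.4.1): OR = (0.438/0.562)/(0.16/0.84) = 4.09, as stated. Power with continuity correction exceeds 99.99%, consistent with the stated >99%. The planning figures are not in question.

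**Inputs.** Arms of 420 and 280 (Section 2.4.1). With 60% at BSA of at least 3% (Section 2.4.2), the skin subset is 0.6 × 420 = 252 on bimekizumab and 0.6 × 280 = 168 on placebo. The lowest placebo PASI90 rate cited is 1.5%, at Week 12. The SAP gives no Week 2 or Week 4 placebo rate, so early rates are assumed.

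**Chance of an empty placebo cell**, (1 − p)^n:

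| True placebo rate | n = 168 | n = 280 |
|---|---|---|
| 0.5% | 43% | 25% |
| 1% | 18% | 6% |
| 1.5% | 8% | 1.5% |
| 2% | 3% | 0.3% |

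For the hierarchy at Week 16: PASI90, 0.90^168 = 2e-8; MDA, 0.857^280 = 2e-19; ACR50, 0.84^280 = 6e-22.

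**Wald test with 25/252 versus 0/168** (the 25 is illustrative). In the treatment-only model, each Newton step changes the placebo logit a by −(1 + e^a). Starting from 0 this gives −2, −3.14, −4.18, and so on, roughly one unit per step without limit. The bimekizumab logit settles at ln(25/227) = −2.21. The standard error is dominated by the placebo term, 1/√(168·e^a).

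| Steps | Placebo logit | Log OR | SE | Wald p |
|---|---|---|---|---|
| 8 | −9.20 | 7.00 | 7.69 | 0.36 |
| 12 | −13.20 | 11.00 | 56.8 | 0.85 |
| 25 | −26.20 | 24.00 | 37,777 | 0.9995 |

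Fisher's exact p for the same table is 2.2e-6.

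**Does the Section 4.1 remedy change this?** In a simulated three-arm data set (168 placebo, 252 bimekizumab, 84 adalimumab; no placebo responders; 20% response on active arms assumed), stopped on a relative-gradient criterion, the Wald p was 0.992 with region and erosion, 0.992 without region and 0.992 without either. The fit met that criterion after 19 iterations, with a log OR near 18 and an SE near 1,900. The non-convergence trigger may therefore never fire.

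**Contradiction within a row.** The formula for the difference in proportions in Section 4.2.2.2 stays stable because the placebo variance term tends to zero: 25/252 − 0 = 9.9%, SE = √(0.0992 × 0.9008/252) = 1.88%, 95% CI 6.2% to 13.6%. This would stand beside a Wald p anywhere from 0.36 to nearly 1.

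**Penalised likelihood, same table.** Firth OR = (25.5/227.5)/(0.5/168.5) = 37.8. The penalised-likelihood-ratio p is 1.5e-6 and the profile 95% CI is 5.2 to about 4,800. The Firth Wald p is 0.011, far from the exact result, so the choice of test within Firth matters.

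**How narrow the failure is.** With 25/252 on bimekizumab, the ordinary Wald p is 0.0045 for one placebo responder, 0.0029 for two and 0.0036 for three.

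**The case against.** The strongest reply is that this is a conditional event on non-confirmatory rows, and most of that stands. The collapse needs exactly zero responders; one is enough for the Wald test to behave. The placebo PASI90 rates in Section 2.4.2 are 9.1%, 9.7% and 1.5%, all at Week 12 or later, with 10% assumed. A reader might infer that the early endpoints will show a p near 1, but no early placebo rate is given, so the documents support only that they could.

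A reader might also infer a threat to the confirmatory result because two listed secondary variables are named. Neither is in Table 4-5, and every affected p-value is nominal.

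Nor does zero on placebo imply a large effect: 5/252 versus 0/168 has a Fisher p of 0.16. The effect would not vanish from the report either, since the secondary tables also carry the rate difference with its interval and the other endpoints carry responder counts. For subgroups, Section 8.1.3 lists odds ratios, differences and intervals but no p-value, so an empty cell would show as an unbounded odds-ratio interval.

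What survives is that, when the empty cell occurs, the prescribed remedy cannot work and the prescribed test gives a wrong answer. That is more than missing detail.

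**Conclusion.** The point holds in conditional form. If a compared arm has no responders, the analysis in Sections 8.1.2, 8.2.2 and 8.3.2.3 has no finite odds ratio, and the Section 4.1 fallback leaves it so. The printed Wald p then depends on the stopping rule and can contradict the difference interval in its own row.

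The chance of this is 8% to 43% per endpoint and visit in the skin subset for true placebo rates of 1.5% down to 0.5%, and lower in the full placebo arm. It rests on assumed early rates and on the SAP's 60% share for the subset. The consequence is limited to nominal p-values and to odds ratios with their intervals. It is worth correcting because the affected rows would mislead, but it does not bear on the trial's confirmatory claims.

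**What to change.** Add to Sections 4.1 and 8.1.2: if a compared arm has zero responders or zero non-responders, or the software reports complete or quasi-complete separation on the treatment term (in subgroup models, on the treatment or interaction term), the same model is fitted with Firth-penalised likelihood. The p-value is the penalised-likelihood-ratio p, the interval is the profile-likelihood interval, and the row is footnoted. State that the Firth Wald p is not used. Keep covariate dropping only for non-convergence caused by sparse region or erosion cells.

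Name this one method and do not offer a choice, so that nothing is left to decide after unblinding. A wider trigger, such as any arm with only a few responders, is not needed for the failure shown here.

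The cost is a sentence in two sections, the FIRTH option with profile-likelihood limits in PROC LOGISTIC, and a footnote. The small downside is that a few rows use a different estimator from the rest of the table.
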